# 7.8 Safety Analyses

All analyses for the safety evaluation variables will be performed on safety set by treatment arm and overall.

- Incidence of TEAEs leading to study drug discontinuation
- Incidence of TEAEs related to study drug leading to study drug discontinuation
- Incidence of TEAEs related to CMB305 leading to study drug discontinuation
- Incidence of TEAEs related to atezolizumab leading to study drug discontinuation
- Incidence of TEAEs leading to death
- Incidence of TEAEs related to study drug leading to death
- Incidence of treatment-emergent dose limiting toxicities by severity
- Incidence of treatment-emergent MEOI by severity

All AEs in safety analysis set will be presented in a data listing.

#### 7.8.2 Deaths

Deaths (and cause of death) will be provided in table and listing.

# 7.8.3 Dosing and Extent of Exposure

The number of injections with LV305, G305, and atezolizumab that patients have received will be used to assess whether the planned study regimen components and the doses are administered.

Number of LV305 dose administered, G305 dose administered, and atezolizumab dose administered will be summarized by frequency and descriptive statistics.

Total cumulative atezolizumab dose (mg) will be summarized and calculated as cumulative dose of atezolizumab administered to the patient over all cycles.

Treatment duration of atezolizumab (weeks) will be calculated as (date of last atezolizumab dose administered - date of first atezolizumab dose administered + 21 days) / 7 days.

The compliance to each study drug (whether entire dose was administered, or missing dose) will also be presented.

CMB305 components (LV305 and G305) and atezolizumab dosing administration will be summarized by treatment arm and all study drug information will be displayed in a listing.

# 7.8.4 Clinical Laboratory Evaluations

Except urinalysis performed only at baseline visit (visit 1), hematology and blood chemistry will be assessed at baseline visit (visit 1), visits 2, 3, 4, 5, 6, 7, 8, 9, 10, 12 and 3-weekly visits during the maintenance phase treatment and follow-up. Laboratory assessments included the following:

- Hematology: WBC count with differential, absolute neutrophil count (ANC), red blood cell (RBC) count, hemoglobin, hematocrit, platelet count, prothrombin time (PT)/partial thromboplastin time (PTT) and international normalized ratio (INR)
- Clinical chemistry (or local panel if inclusive of the following): sodium, chloride, potassium, glucose, blood urea nitrogen (BUN), creatinine, calcium, aspartate aminotransferase (AST)/SGOT, alanine aminotransferase (ALT)/SGPT, total bilirubin, alkaline phosphatase, lactic acid dehydrogenase (LDH), total protein, albumin
- Urinalysis (baseline only): protein, glucose, blood, leukocytes, nitrites, urobilinogen, bilirubin, pH, specific gravity, ketones
- Thyroid function (Screening, Day 84 and every 3 months during the follow-up): T3, T4 and TSH

All local laboratory data will be stored in the database with the units in which they are originally reported. Laboratory data in summary tables and patient data listings will be presented in the international system of units (SI Units). Laboratory data not reported in SI units will be converted to SI units before further processing or data analysis.

Summary statistics (mean, median, standard deviation, and range) of laboratory values for hematology tests and chemistry tests and their changes from baseline values will be tabulated for each visit, by treatment arm. Baseline is defined as the last value prior to first dosing.

Laboratory tests will be graded using NCI-CTCAE v4.03 toxicity grading (see Appendix 1).

Worst change from baseline in toxicity grade for selected laboratory parameters will be presented in shift tables: in each treatment arm, the patient's baseline grade will be cross-

tabulated by the patient's maximum post-baseline grade during the treatment. Data from scheduled and unscheduled visits will be used for finding maximum post-baseline NCI-CTCAE grade of laboratory values.

All laboratory measurements will be presented in a listing.

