Procedures	Timeline – Days	-30 to -1	0	14	21	28	42	56	63	70	84	98	105			
Informed consent/HIPAA ^c	X															
Inclusion/exclusion criteria	X															
Demographics/Medical History	X															
Tumor-specific therapy history	X															
NY-ESO-1 expression on pre-study tumor sample ^d	X															
Enrollment and randomization		X														
Report AEs and SAEs		X	X	X	X	X	X	X	X	X	X	X	X	X	X	
Record any previous concomitant meds	X	X	X	X	X	X	X	X	X	X	X	X	X	X	X	
Vital signs ^e	X	X	X	X	X	X	X	X	X	X	X	X	X	X	X	
Physical exam ^f	X	X	X	X	X	X	X	X	X	X	X	X	X	X	X	
ECG (12-Lead)	X											X				
Tumor staging, by CT scan ^g	X					X				X			X	X		
ECOG	X	X	X	X	X	X	X	X	X	X	X	X	X	X	X	
HIV, HepB, and HepC (5 mL) ^h	X												X ^h	X ^h		
Blood for cellular immunity (55 mL) ⁱ	X	X				X			X		X ⁱ					
Blood for safety labs (10 mL) ^j	X	X	X	X	X	X	X	X	X	X		X	X	X		
Thyroid function tests ^k	X									X			X ^k	X ^k		
Urinalysis	X															
Urine sample for pregnancy test ^l	X	X	X	X	X	X	X	X	X	X		X	X	X		
Study drug: LV305		X	X			X			X							
Study drug: G305					X		X			X			X ^m			
Study drug: atezolizumab		X		X		X		X		X		X ⁿ	X ⁿ	X ⁿ		
Blood for LV305 persistence (8 mL) ^o	X												X ^o	X ^o		
Tumor biopsy ^p	X					X					X ^p			X ^b		
Survival Status															X ^q	
Blood volume per visit (mL)	78	65	10	10	10	65	10	10	65	10	55	10				
Total blood volume	78	14	15	16	17	23	24	25	32	333	38	398				
		3	3	3	3	8	8	8	3		8					

Immune Design
CMB305 (LV305 and G305) and Atezolizumab
Protocol IMDZ-C232; Version 03, Release Date 08Mar2017

Abbreviations: AE = adverse event, CT = computed tomography; ECG = electrocardiogram; ECOG = Eastern Cooperative Oncology Group; HepB = hepatitis B; HepC = hepatitis C; HIPAA = Human insurance Portability and Accountability Act; HIV = Human immunodeficiency Virus; meds = medications; mos = months; PBMC = peripheral blood mononuclear cells; SAE = serious adverse event.

- a. A window of ± 3 days is permitted for Visits 3 through 12. Follow-up phase visits (Visits 13+) will be permitted a window of ± 4 days, Tumor assessments will be permitted a window of ± 1 week.

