- h. An HIV screening test will be repeated on Day 168 to determine if seroconversion has occurred following LV305 injections. If positive, further testing can demonstrate that the normal complement of HIV proteins is not present (unless the patient has developed a true HIV infection).
- i. Blood for immunogenicity will be collected at clinical sites that are trained in peripheral blood mononuclear cells (PBMC) isolation. Baseline samples will be drawn twice to ensure a good yield. At least 55 mL should be collected in 8 Cell Preparation Tubes (CPT)TM tubes for T-cell response assays. See the Lab Manual for processing details.
- j. Initial safety labs are to be performed within 4 days before treatment initiation. On treatment days during the study dosing period, the hematology and clinical chemistry laboratories must also be performed and reviewed before dosing and may be performed up to 48 hours prior to the planned dosing.
- k. Thyroid function tests (triiodothyronine [T₃], thyroxine [T₄], and thyroid stimulating hormone [TSH]) should be taken at initial screening and at least every 3 months while being treated with atezolizumab. As thyroid disorders could occur at any time as a result of atezolizumab treatment, patients should be monitored for changes in thyroid function for clinical signs and symptoms of thyroid disorders (at the start of treatment, periodically during treatment, and as indicated based on clinical evaluation).
- l. Urine pregnancy test must be performed for women of childbearing potential within 72 hours before study drug administration and negative before study drug administration, including during the follow-up period if patients are still receiving booster doses of G305 and/or atezolizumab. Serum pregnancy test may be performed if the site's standard operating procedures allow.
- m. Booster doses of G305 will be given 6 weeks following the Day 84 dose and every 6 weeks thereafter for 1 year (from Day 0) or until disease progression at the staging visits.
- n. Atezolizumab should be continued every 3 weeks for 2 years (from Day 0) or until progression unless toxicity occurs.

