- o. Peripheral blood will be collected at screening, Day 168, and 12 and 24 months after initial injection to test for persistence of LV305. Samples will be assayed for presence of the viral genome by polymerase chain reaction (PCR). Depending on the results through 12 months, annual assessments may continue until 2 consecutive samples show no evidence of LV305 persistence.
- p. The pre-treatment biopsy must be completed ≤ 6 months prior to screening; if not available, a fresh biopsy may be included in the screening process. The tissue biopsy taken on Day 98 can be performed ± 2 weeks from this study visit; however, the patient may opt out of the Day 98 biopsy after a discussion with a physician and documentation in the patient's chart. If a tumor biopsy is not feasible, a biopsy may be done at a subsequent visit with approval provided by the Sponsor.

- q. Once patients have progressed and study drugs are discontinued for more than 30 days, their physicians will be contacted by the sites every 3 months by telephone until the study is completed (last patient, last death in the study) to assess OS. The attending physician will be contacted quarterly or database searched until study completion for identification of subsequent treatments and survival status.

Table 2 Schedule of Events – Control Arm

	Screening	Treatment Phase						Maintenance Phase			Survival Follow-up ^a
Visit	1	2	3	4	5	6	7	8	9	10+	
Timeline – Weeks^a	-4 to 0	0	3	6	9	10	12	14	15	Every 3 wks ^b	Every 3 months (12 wks)
Procedures	Timeline – Days	-30 to -1	0	21	42	63	70	84	98	105	
Informed consent/HIPAA ^c	X										
Inclusion/exclusion criteria	X										
Demographics/medical history	X										
Tumor-specific therapy history	X										
NY-ESO-1 expression on pre-study tumor sample screen ^d	X										
Enrollment and randomization		X									
Report AEs and SAEs		X	X	X	X	X	X	X	X	X	X
Record any previous/concomitant medications	X	X	X	X	X	X	X	X	X	X	X
Vital signs ^e	X	X	X	X	X	X	X	X	X	X	
Physical exam ^f	X	X	X	X	X	X	X	X	X	X	
ECG (12-Lead)	X								X		
Tumor staging, by CT scan ^g	X			X			X			X	
ECOG	X	X	X	X	X	X	X	X	X	X	
HIV, HepB, and HepC (5 mL)	X										
Blood for cellular immunity (55 mL) ^h	X	X		X		X		X			
Blood for safety labs (10 mL) ⁱ	X	X	X	X	X		X		X	X	
Thyroid function tests ^j	X						X			X ^j	
Urinalysis	X										
Urine sample for pregnancy test ^k	X	X	X	X	X		X		X	X	
Study drug: atezolizumab		X	X	X	X		X		X	X ^l	
Tumor biopsy ^{m & b}	X			X				X ^m		X ^b	

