8.2.2 Treatment Phase (Weeks 0-12 Treatment Visits, Study Days 0 to 84)

The following procedures will be performed at all study visits for subjects in both treatment arms:

1. AEs and SAEs (including MEOIs)
2. Concomitant Medications
3. Vital Signs (temperature, HR, resting BP) obtained pre-dose and 30 minutes, post-dose. For the first atezolizumab infusion, the patient's vital signs (HR, respiratory rate, BP, and temperature) should be measured within 15 minute of the infusion, during the 60-minute infusion (every 15 [± 5] minutes), and 30 minutes after the infusion. For subsequent infusions, vital signs do not need to be obtained during the infusion if the prior infusion was tolerated without symptoms.
4. Physical examination: simple targeted physical examination
5. ECOG status
6. Urine pregnancy test for FCBP on treatment days. Note: pregnancy test must be performed within 72 hours before study drug administration and negative before study drug administration.
7. Blood samples (10 mL) for safety laboratory evaluations within 4 days before treatment initiation and up to 48 hours before each subsequent dose.

The following procedures will occur at select study visits according to the study visit schedule provided in [Table 1](#) and [Table 2](#):

- Blood samples will be collected at selected sites on Study Days 0, 42, and 70 for immunological assessments including cellular immunity (55 mL).
- A blood sample will be collected at Study Day 84 for thyroid function tests.
- Tumor Staging: includes CT scans to evaluate progression per RECIST/irRC will be performed every 6 weeks. MRI, bone scans or PET/CT will only be performed if clinically necessary.
- Tumor biopsy on Days 0 and 42
- Patients in the combination treatment arm will receive study drug LV305 at Study Day 0, Week 2, 6, and 10; G305 will be administered at Weeks 4, 8, and 12.
- Atezolizumab will be administered every 3 weeks (Weeks 0, 3, 6, 9, and 12).

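### The combination arm has 9 scheduled post-baseline safety-lab draws by Day 105 and the control arm 5, so the by-arm worst-grade lab table in SAP 7.8.4 would tend to show more lab toxicity in the combination arm even if true toxicity were equal

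*SAP*

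**What the plan says.** For hematology and chemistry, SAP 7.8.4 plans shift tables by arm for selected parameters, setting baseline grade against the highest grade reached during treatment. On which values feed that maximum it says: "Data from scheduled and unscheduled visits will be used for finding maximum post-baseline NCI-CTCAE grade of laboratory values". On the reference point it says: "Baseline is defined as the last value prior to first dosing". It contains no restriction to days shared by the arms and no caveat about sampling frequency.

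Protocol 8.2.2 ties the draws to dosing: "Blood samples (10 mL) for safety laboratory evaluations within 4 days before treatment initiation and up to 48 hours before each subsequent dose". The notes to both schedules of events add that on treatment days "the hematology and clinical chemistry laboratories must also be performed and reviewed before dosing". The Day 0 draw is therefore a baseline value in both arms.

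SAP 7.8.4 gives the lab visits after screening as "visits 2, 3, 4, 5, 6, 7, 8, 9, 10, 12 and 3-weekly visits during the maintenance phase treatment and follow-up", without distinguishing the arms.

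Protocol 10.2.2.5 requires the highest grade per patient to be tabulated for laboratory measurements and states that safety is not formally tested. SAP 7.9 says parameters will be quantified for direct between-arm comparison where possible, and treats such comparisons as exploratory.

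**The concern.** The extra draws are not random. They fall on Days 14, 28, 56 and 70, when only CMB305 is given, so sampling intensity follows treatment assignment. A per-patient maximum depends on how often one looks: an abnormality that comes and goes between shared days can be recorded in the combination arm and missed in the control arm.

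Safety is a secondary endpoint, and CMB305 is an add-on to a common backbone. A reader who sees higher worst grades in the combination column will naturally attribute them to CMB305. Part of such a difference could come from the schedule, and nothing in the planned table would reveal that.

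**Working it through.** **Inputs.** Safety-lab marks in Table 1 (combination) and Table 2 (control) of the protocol, repeated in the SAP:

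- Combination, after the pre-dose Day 0 draw: Days 14, 21, 28, 42, 56, 63, 70, 84, 105, which is 9 draws.
- Control, after the pre-dose Day 0 draw: Days 21, 42, 63, 84, 105, which is 5 draws.

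**Check against the plan's own figures.** The tables state cumulative blood volumes of 398 mL and 350 mL by Day 105. Rebuilding them from the marks:

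- Combination: screening 5 + 55 + 10 + 8 = 78; four later cellular-immunity draws 4 × 55 = 220; Day 0 plus 9 safety draws 10 × 10 = 100. Total 398 mL.
- Control: screening 5 + 55 + 10 = 70; 4 × 55 = 220; Day 0 plus 5 safety draws 6 × 10 = 60. Total 350 mL.

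Both match, so the counts of 9 and 5 are confirmed.

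**After Day 105.** Both arms have 3-weekly visits. The first G305 booster falls on Day 84 + 42 = 126, which is also 105 + 21, so boosters add no further lab days. Days 126 to 357 in steps of 21 give 12 more draws, and Days 126 to 714 give 29.

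| Treated to | Combination | Control | Ratio |
|---|---|---|---|
| Day 84 | 8 | 4 | 2.00 |
| Day 105 | 9 | 5 | 1.80 |
| 1 year | 9 + 12 = 21 | 5 + 12 = 17 | 1.24 |
| 2 years | 9 + 29 = 38 | 5 + 29 = 34 | 1.12 |

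If time on treatment is assumed exponential, using the SAP section 4 median PFS values as a proxy, expected draws are 8.7 versus 5.8 (ratio 1.51) at a median of 3 months and 13.3 versus 9.9 (1.34) at 5.2 months.

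**Size under independent draws.** With the same per-draw risk p in both arms, the chance of at least one graded value in n draws is 1 − (1 − p)^n. The documents give no p; the values below are assumptions.

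| p | By Day 105 (n = 9 vs 5) | Excess | To 1 year (n = 21 vs 17) | Excess |
|---|---|---|---|---|
| 2% | 16.6% vs 9.6% | 7.0 points | 34.6% vs 29.1% | 5.5 points |
| 5% | 37.0% vs 22.6% | 14.4 points | 65.9% vs 58.2% | 7.8 points |
| 10% | 61.3% vs 41.0% | 20.3 points | 89.1% vs 83.3% | 5.7 points |

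**Size when abnormalities last.** As a sensitivity check, one episode per patient was simulated, with onset uniform over Days 0 to 105 and exponential duration. The figures are the chance that such an episode is present on at least one scheduled draw by Day 105.

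| Mean duration | Combination | Control | Ratio |
|---|---|---|---|
| 3 days | 24.6% | 14.3% | 1.72 |
| 7 days | 46.1% | 31.5% | 1.46 |
| 14 days | 65.0% | 51.9% | 1.25 |
| 42 days | 85.6% | 78.7% | 1.09 |
| Persistent (1000 days) | 99.3% | 99.0% | 1.00 |

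**Visit numbering.** Visits 2 to 10 and 12 match the combination arm's lab marks. In the control arm, labs fall at Visits 2, 3, 4, 5, 7, 9 and 10 onward. Visits 6 and 8 (Days 70 and 98) have no safety lab, and Visit 3 is Day 21 rather than Day 14.

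**The case against.** The strongest reply is that this is a descriptive table with no test, no between-arm estimate and no decision attached: the safety stopping rule counts DLTs. That is correct, and a reader who inferred that the SAP formally compares worst grades would be going beyond it. It does not remove the problem, because side-by-side columns are read by eye and these carry no warning.

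Second, the maximum over 9 draws is not necessarily larger than over 5. It is equal whenever the worst grade also appears on a shared day. This stands; the documents support a tendency, not a certainty that CMB305 will look more toxic.

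Third, the 7 to 20 points rest on independent draws and stop at Day 105, whereas the table covers the whole treatment period and serial values in one patient are correlated. This also stands. Those figures are illustrations and should not be read as the bias in the planned table.

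Fourth, the shift table might be taken as the main summary of lab toxicity. The documents do not say so. It covers selected parameters only. SAP 7.8.4 also plans by-visit values and changes from baseline and a full listing, and SAP 5.2 sends clinically significant abnormalities to the adverse-event data. The by-visit summaries do not take a maximum over draws.

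Fifth, replacing the all-values table would conflict with protocol 10.2.2.5 and could hide real transient effects, including those on Day 14, the first look after LV305. Over-reporting in the experimental arm is also the cautious direction for safety. This is a good argument for keeping that table, but not for leaving it unannotated or as the only worst-grade view.

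**Conclusion.** The point holds as a limitation of a descriptive safety table. The 9 versus 5 count is exact, SAP 7.8.4 carries it into a by-arm maximum without adjustment or caveat, and under equal true toxicity the expected tilt can only be against the combination arm.

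Its size is not determined by the documents. It could be material for short-lived abnormalities in patients treated for only a few months. It shrinks with longer treatment and with within-patient correlation, and it all but vanishes for persistent abnormalities. A reader might infer that any excess in the combination column would be an artefact; the documents do not support that either, since a true CMB305 effect and the sampling effect would appear in the same cells. No efficacy conclusion or stopping rule depends on this table.

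**What to change.** In SAP 7.8.4:

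1. Keep the all-values worst-grade shift table. Footnote it with the number of draws per patient by arm and a statement that scheduled sampling differs between arms.
2. Add a by-arm worst-grade shift table restricted to the scheduled days common to both arms (Days 21, 42, 63, 84 and 105, then 3-weekly), and use it for any between-arm reading. This gives 5 versus 5 scheduled draws by Day 105. The ±3-day visit windows around Days 14, 21 and 28, and around 56, 63 and 70, do not overlap, so values can be assigned by nominal visit.
3. List the control-arm lab visits separately, by day as well as visit number.

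The cost is SAP wording and one extra table, with no change to visits or blood draws. The common-day table omits abnormalities seen only on Days 14, 28, 56 or 70 or at unscheduled visits; these remain in the all-values table and the listing.

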## 7.8.5 Vital Signs

Vital sign measurements include temperature, pulse (heart rate), respiratory rate, resting systolic and diastolic blood pressure. Temperature, pulse (heart rate), respiratory rate, resting systolic and diastolic blood pressure will collected at screening visit (visit 1), and all visits through weeks 0-12 treatment, post-CMB305 treatment, and maintenance phase.

On the day of each dosing, vital signs will be obtained pre-dosing and 30 minutes after dosing. For the first atezolizumab infusion, the patient's vital signs (HR, respiratory rate, BP, and temperature) should be measured within 15 minutes of the infusion, during the 60-minute infusion (every 15 [ $\pm$  5] minutes), and 30 minutes after the infusion. For subsequent infusions, vital signs do not need to be obtained during the infusion if the prior infusion was tolerated without symptoms.

For first infusion, measurements collected in all time points will be summarized in table. For subsequent infusion, only the measurements collected at time point pre-dosing and 30 minutes after dosing need be summarized.

Summary statistics (mean, median, standard deviation, and range) of baseline and post-baseline vital signs measurements (temperature, pulse, respiratory rate, resting systolic and diastolic blood pressure), as well as the changes from baseline, will be tabulated for each visit, by treatment arm. Baseline is defined as the last value prior to initial LV305 or atezolizumab dosing, whichever occurs first.

All vital signs measurements will be presented in a listing. The visits with clinically significant abnormalities in vital sign measurements will be flagged in the vital signs listing.

# 7.8.6 ECG

12-Lead ECG measurements collected in both scheduled and unscheduled visits will be presented in data listings.

#### 7.8.7 Physical Findings

Physical examination abnormalities will be included in the adverse event (abnormalities after the start of study drug) or medical history (abnormalities before the start of study drug) summaries and listings

#### 7.8.8 Pregnancy Test

Pregnancy test will be performed at baseline (visit 2) and at each dosing visit. Pregnancy data will be presented in a listing.

#### 7.8.9 ECOG Performance Status

ECOG performance status will be summarized by visit and presented in a listing.

# 7.8.10 Prior and Concomitant Medications

Verbatim terms of prior and concomitant medications will be coded using the most current version of the World Health Organization (WHO) Drug Dictionary (3Q 2018 or newer).

All concomitant medications will be summarized by ATC class and preferred term and all prior and concomitant medications will be presented in a listing. A patient with more than one different medication in a medication class will be counted only once in the total of patients taking that medication class. A patient having the same medication more than once during the study will be counted only once in the number of patients with that medication.

**Concomitant medication/treatment** is any medication/treatment with start date on or after the initial dosing of LV305 or atezolizumab, whichever occurs first.

**Prior medication** is defined as any medication with start date on or before the first day of study drug (LV305 or atezolizumab, whichever occurs first), or medication with start date missing.

Any medication/treatment which cannot be identified as prior or concomitant will be considered prior and concomitant.

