6.2 Exclusion Criteria

Patients meeting any of the following criteria will not be eligible for participation in the study:

1. Investigational therapy within 4 weeks prior to CMB305 dosing
2. Prior administration of other NY-ESO-1-targeting immunotherapeutics
3. Prior treatment with immune checkpoint therapies, including anti-CTLA-4, anti PD-1, and anti PD-L1 therapeutic antibodies, or any other antibody or drug targeting T cell costimulation
4. Treatment with systemic immunostimulatory agents (including but not limited to IL-2) within 4 weeks or five half-lives of the drug, whichever is shorter, prior to first dose
5. Significant immunosuppression from:
 - a. Concurrent, recent (≤ 3 weeks prior to the first schedule dosing) or anticipated need for treatment with systemic corticosteroids (the use of physiologic doses of corticosteroids may be approved after consultation with the Sponsor). The use of topical or inhaled corticosteroids and mineralocorticoids (e.g., fludrocortisone) is allowed.
 - b. Other immunosuppressive medications (≤ 3 weeks prior to the first scheduled dosing) including but not limited to cyclophosphamide, azathioprine, methotrexate, thalidomide, and anti-tumor necrosis factor (anti-TNF) agents or conditions such as common variable hypogammaglobulinemia.
6. Other cancer therapies, including chemotherapy, radiation, biologics or kinase inhibitors within 3 weeks prior to the first scheduled dosing
7. Has received colony stimulating factors (CSFs; including granulocyte [G]-CSF, granulocyte-macrophage [GM]-CSF, or recombinant erythropoietin) within 4 weeks prior to the first scheduled dosing
8. Psychiatric, other medical illness, or other condition that in the opinion of the Investigator prevents compliance with study procedures or ability to provide valid informed consent
9. History of autoimmune disease, including but not limited to myasthenia gravis, myositis, autoimmune hepatitis, systemic lupus erythematosus, rheumatoid arthritis, inflammatory bowel disease, vascular thrombosis associated with antiphospholipid syndrome, Wegener's granulomatosis, Sjögren's syndrome, Guillain-Barré syndrome, multiple sclerosis, vasculitis, or glomerulonephritis (see [Appendix E](#) for a more comprehensive list of autoimmune diseases)
 - Patients with a history of autoimmune-related hypothyroidism on a stable dose of thyroid replacement hormone may be eligible for this study.

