 - Patients with controlled Type 1 diabetes mellitus on a stable insulin regimen may be eligible for this study.
10. History of idiopathic pulmonary fibrosis (including pneumonitis), drug-induced pneumonitis, organizing pneumonia (i.e., bronchiolitis obliterans, cryptogenic organizing pneumonia), risk of pulmonary toxicity, or evidence of active pneumonitis on screening chest CT scan. History of radiation pneumonitis in the radiation field (fibrosis) is permitted.

11. Significant cardiovascular disease, such as New York Heart Association cardiac disease (\geq Class II), myocardial infarction within the previous 3 months prior to study treatment, unstable arrhythmias, or unstable angina
12. Inadequate organ function, including the following:
 - a. Marrow: ANC \leq 1500/mm³, platelets $<$ 75,000/mm³, or hemoglobin (Hb) $<$ 10 g/dL
 - b. Hepatic: ALT, and AST $>$ 2.5 \times ULN (OR \geq 5 \times ULN for subjects with liver metastases), total serum bilirubin $>$ 1.5 \times ULN (OR direct bilirubin \geq ULN for patients with total bilirubin levels $<$ 1.5 \times ULN; patients with Gilbert's Disease may be included if their total bilirubin is $<$ 3.0 mg/dL)
 - c. Renal: creatinine $>$ 1.5 \times ULN
 - d. Other: prothrombin time (PT), international normalized ratio (INR), or partial thromboplastin time (PTT) $>$ 1.5 \times ULN
13. Uncontrolled pleural effusion, pericardial effusion, or ascites requiring recurrent drainage procedures (once monthly or more frequently). Patients with indwelling catheters (e.g., PleurX[®]) are allowed.
14. Uncontrolled tumor-related pain. Patients requiring pain medication must be on a stable regimen at study entry. Symptomatic lesions amenable to palliative radiotherapy (e.g., bone metastases or metastases causing nerve impingement) should be treated prior to enrollment. Asymptomatic metastatic lesions whose further growth would likely cause functional deficits or intractable pain (e.g., epidural metastasis that is not presently associated with spinal cord compression) should be considered for loco-regional therapy if appropriate prior to enrollment.

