#### 7.2.2 Partial Dates for Concomitant Medication

For medications with incomplete dates, imputation will be used to convert to a complete date. Imputed dates will be used to determine Study Day.

Partial medication start dates will be imputed as follows:

- 1. Only the year is reported: If the subject started to receive study drug in the year reported, then the date of the first dose of study drug will be used as the starting date of the medication. Otherwise, January 1 will be used as the start of the medication.
- 2. The month and year are reported: If the subject started to receive study drug during the month and year reported, then the date of first dose of study drug will be used as the starting date of the medication. Otherwise, the first day of the month will be used as the start of the medication.

Partial medication end dates will be imputed for non-ongoing medications as follows:

1. Only the year is reported: If the subject stopped to receive study drug in the year reported, then the date of the last dose of study drug will be used as the end date of the medication. Otherwise, December 31 will be used as the end of the medication.

2. The month and year is reported: If the subject stopped to receive study drug during the month and year reported, then the date of last dose of study drug will be used as the end date of the medication. Otherwise, the last day of the month will be used as the end of the medication.

If an imputation results in an imputed start date after the stop date, the start date will be set to the day prior to the stop date.

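### SAP 7.8.10 defines a concomitant medication by start date alone, so fully dated drugs carried over from before first dose are left out of the by-arm summary

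*SAP*

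**What the plan says.** SAP 7.8.10 gives two definitions, both resting on the start date. A concomitant medication or treatment "is any medication/treatment with start date on or after the initial dosing of LV305 or atezolizumab, whichever occurs first". A prior medication "is defined as any medication with start date on or before the first day of study drug", and a drug with a missing start date is also prior.

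On display, the same section says: "All concomitant medications will be summarized by ATC class and preferred term and all prior and concomitant medications will be presented in a listing". So concomitant drugs are tabulated and listed, while drugs that are only prior are listed.

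It closes with a catch-all: "Any medication/treatment which cannot be identified as prior or concomitant will be considered prior and concomitant".

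SAP 7.2.2 covers partial dates. If only the year is known and it is the first-dose year, or month and year are known and match those of first dose, "then the date of the first dose of study drug will be used as the starting date of the medication". End dates are handled too: "Partial medication end dates will be imputed for non-ongoing medications as follows".

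The protocol expects some drugs to be in use at entry. Section 6.2 says "Patients requiring pain medication must be on a stable regimen at study entry". It also allows for stable thyroid replacement, stable insulin, bisphosphonates, stable anticonvulsants, and topical or inhaled steroids, and says of systemic steroids that "the use of physiologic doses of corticosteroids may be approved after consultation with the Sponsor".

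**The concern.** A concomitant medication table should show what patients were taking while on study drug. A rule based on start date shows what they began after first dose, which is a different set. Long-standing background treatment is the part most likely to be lost, because it is already running on Day 0.

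Protocol 7.4.2 excludes certain drugs during treatment because they could change the activity or safety of atezolizumab. In an open-label two-arm trial, a reader would use the by-arm medication table to see whether background treatment was similar. Under this rule the table omits carried-over use, depends on how completely a start date was recorded, and has no point after the last dose at which counting stops.

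**Working it through.** The plan states no figure here, so the check applies the written rule to test cases.

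**Inputs.** Day 0 is first dose. S is start day, E is end day, L is day of last dose. L = 200 is assumed for illustration. The 30-day limit comes from the treatment-emergent adverse event window in SAP 7.8.1.

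**SAP 7.8.10 as written.** Prior if S ≤ 0 or S is missing. Concomitant if S ≥ 0.

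**Overlap rule.** Concomitant if (ongoing or E ≥ 0) and S ≤ L + 30 = 230. A missing S passes the start condition.

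| History | S | E | SAP 7.8.10 | Concomitant by overlap? |
|---|---|---|---|---|
| Stopped before first dose | −60 | −10 | prior only | no |
| Carried over, ongoing | −60 | ongoing | prior only | **yes** |
| Carried over, stopped on treatment | −60 | 100 | prior only | **yes** |
| Started at first dose | 0 | 20 | both | yes |
| Started on treatment | 50 | 60 | concomitant | yes |
| Started 15 days after last dose | 215 | 220 | concomitant | yes |
| Started 200 days after last dose | 400 | 420 | concomitant | **no** |
| Start missing, ongoing | missing | ongoing | prior only | **yes** |
| Year-only start in first-dose year, ongoing | imputed to 0 | ongoing | both | yes |

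Four of nine change (bold): three on-treatment exposures are omitted as written, and one off-treatment drug is counted.

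**Catch-all.** It reaches only drugs that cannot be classified. A known start before first dose makes a drug prior, and so does a missing start, so neither is unclassifiable. By contrast, SAP 7.2.1 treats an adverse event with a completely missing start date as treatment-emergent.

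**Date quality.** Compare rows two and nine. If both describe one drug begun in the calendar year of first dose, the complete date removes it from the table and the year-only date puts it in.

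**Upper limit.** SAP 7.8.1 stops 30 days after the last dose unless a later event is related to study drug. SAP 7.8.10 has no stop, and both schedules of events mark medication recording in the Survival Follow-up column. Protocol 5.1 and 6.3 also direct that non-protocol systemic anti-cancer therapy given before radiographic progression be recorded as concomitant medication. A patient who stops for toxicity and starts such therapy much later would be counted.

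**Other tables.** Protocol 10.2.2.2 includes medication history among the items to be summarized by treatment group. SAP 7.5 covers demographics, cancer history, medical history and prior tumor therapy, but no general medication summary. SAP section 8 lets the SAP prevail where the two differ.

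**The case against.** The strongest reply is that nothing is lost: every prior and concomitant drug is in the listing, the table is descriptive, and SAP 7.9 treats between-arm comparisons as exploratory. That is correct. It limits the consequence but does not make the table right.

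Second, Protocol 10.2.2.2 already provides for medication history, and the table shells and dataset specifications are in separate documents. Whether SAP silence counts as a discrepancy under section 8 is arguable. What stands is that the summary was not carried over.

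Third, late contamination is limited. Protocol 8.2.3.1 and 8.2.3.2 restrict concomitant medication reporting at the three-weekly return visits to related drugs. Protocol 8.2.4 describes survival follow-up as a check on survival status and subsequent treatment, and SAP 7.8.11 summarizes subsequent anti-cancer therapy separately. This reduces the number of late drugs but does not remove them, because any that are recorded still meet the definition.

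A reader might also infer that the rule hides substantial background steroid use. The documents do not support that. Exclusion 5a restricts systemic steroids at entry apart from a Sponsor-approved physiologic dose. Protocol 7.4.1 bars systemic steroids for four weeks before dosing, while 7.4.2 words its prohibition as above 10 mg/day prednisone equivalent. These passages conflict and must be reconciled. The point does not need them, since analgesics, thyroid replacement, insulin, bisphosphonates and anticonvulsants show the same gap.

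**Conclusion.** The point holds as a defect in a stated definition. For a fully dated drug begun before first dose and continued, omission from the by-arm table is certain under the written rule. It is equally certain for an ongoing drug with no start date. Counting of a recorded drug started long after the last dose is also certain.

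The number of patients affected cannot be given, because the documents contain no medication-use data; four of nine counts constructed histories only. A reader might infer that the table is tilted toward the arm that stops treatment sooner, but nothing in the documents shows a difference in stopping time or late drug use. A reader might also suspect an effect on PFS through censoring at new anti-cancer therapy. That rule in SAP 5.1.1.1 does not refer to the concomitant definition. PFS, OS, PFR at 6 months and adverse event incidence are untouched. This is an inexpensive correction to a descriptive safety summary.

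**What to change.** In SAP 7.8.10:

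- Define prior as started before first dose.
- Define concomitant as taken at any time from first dose to 30 days after the last dose of any study drug: ongoing or ended on or after first dose, and started no later than last dose plus 30 days. State that a drug may be both.
- Treat a missing start date as both, unless the end date is before first dose.
- Show drugs started more than 30 days after last dose separately.

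In SAP 7.5, either carry over the medication-history summary from Protocol 10.2.2.2 or record its omission as a change.

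Reconcile Protocol 6.2 (exclusion 5a), 7.4.1 and 7.4.2 on steroids.

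The cost is SAP wording and one derived flag. Screening already records current medications, and SAP 7.2.2 already handles end dates and ongoing status, so carried-over drugs need no new collection. The flag cannot recover drugs never recorded because of the related-only reporting in Protocol 8.2.3.1 and 8.2.3.2; a footnote to the table should say so.
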